### 1.2 SCHEMA

# Figure 1: Study Flow Chart

# Screening

- Obtain informed consent
- •Assess inclusion/exclusion criteria
- Capture baseline demographics, medical history and concomitant medications
- Collect clinical assessments (height, weight, previous X-Ray interpetation if available)

# **Enrollment**

- Affirmation of informed consent and enrollment (Only if screening visit is independent of procedure visit)
- ENvizion nasoenteral feeding tubes will be placed in 5 run-in subjects prior to enrollment of the remaining subjects
- •Enroll the rest of the subjects

# Procedure (within 2-days of screening)

- Collect pre-procedure vital signs
- •Place NasoEnteral Tube using ENVUE System
- Collect procedure information (including number of tube replacement events)
- •Confirm placement via X-Ray (within 5 hours)
- Assess for adverse events and device related side effects

# Follow-up (20-48 hours post procedure)

- Collect vital signs
- Confirm tube location using ENVUE System and X-Ray
- •Collect information regarding tube migration and reposition
- •Assess for adverse events or device related side effects

# Study Exit

Version 1.3 NUTRI-002 July 11, 2018

# SCHEDULE OF ACTIVITIES (SOA)

The study schedule for this evaluation is presented below in **Table 1**.

**Table 1: Study Schedule** 

Procedures, Evaluations and	Study Visits			
Tests	Screening	Procedure (Within 2 days of Screening Visit)	Follow-up (20-48 hours after Procedure Visit)	
Informed Consent	X	X 		
Inclusion/Exclusion Criteria	Χ			
Demographics	Χ			
Medical History (Acute and Past)	X			
Concomitant Medications 	Х			
Examinations				
Targeted Physical Exam	Χ			
Vital Signs		X	X	
ENvizion™ nasoenteral tube		Х		
Placement		Λ		
Confirm Anatomical Location				
ENVUE System			X	
Abdominal and/ or thoracic X-		X 6	X	
ray 		^	^	
Adverse Events		X	X	

<sup>3 Affirmation of informed consent is only required if procedure visit is independent of screening visit.

<sup>4 Limited to sedatives/any medication with sedative effect, anticoagulants and prokinetic agents.  Additional X-Rays may be taken if clinically indicated.  Within five hours of placement.

Version 1.3 NUTRI-002 July 11, 2018

# 2 STATISTICAL CONSIDERATIONS

# 2.1 STATISTICAL HYPOTHESES

There is no formal statistical hypothesis for the primary endpoint of this feasibility trial. The primary endpoint is defined as procedure success, e.g., NET tube can be placed in the correct anatomical position without occurrence of guidance-related adverse events.

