# PROTOCOL SUMMARY

1.1 SYNOPSIS			
STUDY TITLE	A Feasibilty Study to Evaluate the Clinical Safety of ENvizion™ Nasoenteral Feeding Tube Placement using the ENvizion™ ENVUE System in Patients.		
PROTOCOL NUMBER	NUTRI-002		
DEVICE DESCRIPTION	The ENvizion™ ENVUE™ System is designed to aid qualified operators in the placement of the ENvizion™ NasoEnteral Tube™ of 10 Fr to 12 Fr into the stomach or small intestine of patients requiring enteral feeding. The ENVUE System is intended as an adjunct to current placement practices for assisting clinical practitioners who place feeding tubes in adult patients.		
	The ENvizion™ NasoEnteral Tube has been specifically designed for use with the ENVUE™ System and is intended for placement in the stomach or small intestine. It is intended for use in adult patients who require intermittent or continuous feedings via the nasogastric or nasoenteric route.		
STUDY OBJECTIVES	The objective of this study is to assess the safety of the ENVUE System as an adjunct to current practices for placement of nasoenteral feeding tubes.		
STUDY DESIGN	The study is a prospective, single center, non-randomized clinical trial in patients that require placement of a nasoenteral feeding tube as a result of their current medical condition.		
NUMBER OF SUBJECTS AND SITES	Up to fifty (50) subjects and at least forty (40) will complete the Procedure Visit (NasoEnteral Tube placement procedure, section 1.3) at a single center by at least five operators. This number (40-50 subjects) does not include screen failures. Envizion nasoenteral feeding tubes will be placed in 5 run-in subjects prior to enrollment of the remaining subjects. All enrolled subjects (run-in subjects and trial subjects) will be included in the final analysis.		
DURATION OF PARTICIPATION/STUDY	Each patient's individual participation will last approximately 20-48 hours.  It is expected the entire study will take approximately two (2) months to complete.		
STUDY ENDPOINTS	Primary Endpoint:		
	Procedure success: Nasoenteral tube (NET) can be placed in the correct anatomical position without occurrence of guidance-related adverse events.		

Version 1.3 NUTRI-002 July 11, 2018

	Additional Assessments:				
	Procedure Metric s: Number of placement attempts required				
	Safety: Adverse Events				

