Sample Size Considerations	There is no statistically based sample size for this study which is being conducted to obtain confirmatory evidence to support the safety of using the ENVUE System as an adjunct to current placement practices for nasoenteral feeding tubes. Forty (40) to Fifty (50) subjects (includes run-in subjects) completing the Procedure Visit (NasoEnteral Tube placement procedure) will provide evidence that the NET tube guidance system does not present new or different safety issues as compared to the predicate (confirmatory study). If less than 35 patients will complete the Follow-up Visit (confirmation of tube tip anatomical location), an enrollment of another 5 patients will be considered.				
SCHEDULED VISITS	This study is an acute safety assessment of the ENVUE System covering the guidance functionality of the System.  Screening The screening visit will occur at time zero and will assess eligibility for the study and				
	obtain informed consent.  Procedure  The study procedure may occur within two days of screening. Informed consent will be affirmed and the patient will be considered enrolled.				
	Final Follow Up The final follow-up visit will occur 20-48 hours following the procedure.				
Inclusion Criteria	
 
Patients must be ≥21 years of age
 
Patients must require placement of a nasoenteral feeding tube
 
Patients have an endotracheal tube, OR         
 
Do not have an endotracheal tube but are sedated and/or classified as obtunded¹ at the time of placement
 
 
 
Patients or legal authorized representative must be able to understand and
 
				
	adhere to all protocol procedures and be willing and able to provide written informed consent 				

Obtundation level evaluation is based on Glasgow-Coma scale with a score of between 9 and 12. Sedation level is based on Richmond Agitation-Sedation Scale (RASS) score of -2 or less.
Consent may be provided by patient's legal authorized representative.

 NUTRI-002
 Version 1.3

 July 11, 2018

	Patients must not have a history of:				
EXCLUSION CRITERIA	
 
Esophageal varices or ulcers
 
				
	
 
Upper airway obstruction
 
				
	
 
Upper GI stenosis or obstruction
 
				
	
 
Trauma involving sinuses, nares face or neck that would prevent NG
 
				
	or oral tube insertion				
	
 
Deformities of the sinus cavities and/or skull base
 
				

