	
 
Esophageal cancer or neoplasm
 
				
	Patients must not have a significant concomitant illness that would adversely				
	affect their participation in the study				
	Female patients who are pregnant or lactating				
STATISTICAL ANALYSIS	All data will be reported using summary statistics.				
OTHER CONSIDERATIONS	No core lab will be charted for this study; thus, judgements regarding placement will be based on the investigator's assessment of X-Ray images. Assessments of relatedness of any noted adverse events to the study device will be adjudicated by a Clinical Events Committee (CEC). No DSMB will be chartered for this study based on the well-understood safety profile.				
US REGULATORY STATUS	The ENVUE System is considered a non-significant risk investigational device in the United States.				

Version 1.3 NUTRI-002 July 11, 2018

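### Does the primary endpoint need to name the X-ray and the adverse-event window that decide procedure success?

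*Combined protocol and SAP*

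**What the plan says.** The synopsis (1.1, Study Endpoints) calls the primary endpoint procedure success and defines it by whether the tube "can be placed in the correct anatomical position without occurrence of guidance-related adverse events". Section 2.1 repeats this, introduced by *e.g.*: "NET tube can be placed in the correct anatomical position without occurrence of guidance-related adverse events". Neither place names a visit, an image or a window.

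The schema (1.2) has, at the procedure, "Confirm placement via X-Ray (within 5 hours" of placement), and at follow-up, 20-48 hours later, "Confirm tube location using ENVUE System and X-Ray" and "Collect information regarding tube migration and reposition". Table 1 marks an X-ray and an adverse-event assessment at both visits. A footnote permits further X-rays when clinically indicated.

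Under Other Considerations the synopsis states that "judgements regarding placement will be based on the investigator's assessment of X-Ray images", and that a Clinical Events Committee rules on whether adverse events are related to the device. The sample size text (synopsis and 2.2) describes the Follow-up Visit, in parentheses, as the one where the location of the tube tip is confirmed. That description sits in a rule for considering five more patients if fewer than 35 complete follow-up.

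Section 2.4 has procedure success calculated in every population, with other results summarised descriptively. The additional assessments are adverse events and "Number of placement attempts required".

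**The concern.** Both components of a single composite endpoint are measured twice, and the definition does not say which measurement decides. The plan expects tubes to move, since it collects migration and repositioning. A tube in place at five hours and displaced the next day would be a success on one image and a failure on the other. A tube first misplaced and then repositioned would be the reverse. A guidance-related event first noted at follow-up raises the same question. The parenthetical description of the Follow-up Visit seems to point to the later image, the schema's procedure step to the earlier one.

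The study is meant to show that the system "does not present new or different safety issues as compared to the predicate", and with no test planned the observed rate is the whole primary result. If its definition were open, someone could choose the image or window after seeing the data.

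**Working it through.** The plan contains no power, target rate or computed sample size to reproduce; the synopsis says the sample size has no statistical basis. The check is therefore mainly a comparison of texts, followed by the size of the effect.

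**1. Which image?**
- The endpoint is named for the procedure, and its verb is about placing the tube.
- Other Considerations speaks of judging placement on X-ray.
- The schema uses the same noun, placement, for the X-ray within five hours. For the 20-48 hour X-ray it speaks of tube location, next to migration and repositioning.
- Table 1 schedules both X-rays, so each visit confirms location for its own purpose. The parenthesis in the sample size text says what happens at follow-up. It does not define the endpoint, and it does not say that follow-up alone confirms location.

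These passages are compatible, and the reading they support is the X-ray within five hours.

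**2. Which adverse-event window?** The clause excludes any occurrence of a guidance-related event and sets no time limit. Events are collected at both visits, and the synopsis describes the whole study as an acute safety assessment. Leaving out follow-up events would need a restriction that the text lacks.

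**3. Is *e.g.* a problem?** The synopsis gives the same definition outright, without *e.g.* The abbreviation in 2.1 is a slip for *i.e.*

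**4. Effect if the later image were used instead.** Suppose all tubes are correct at five hours, no events occur, and k tubes are out of position at 20-48 hours. Success on the first image is 100%. On the second it is (N − k)/N:

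| k | N = 40 | N = 50 |
|---|---|---|
| 1 | 39/40 = 97.5% | 49/50 = 98.0% |
| 2 | 38/40 = 95.0% | 48/50 = 96.0% |
| 4 | 36/40 = 90.0% | 46/50 = 92.0% |

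In the reverse case, two of 40 tubes wrong at first and then repositioned give 38/40 = 95.0% on the first image and 40/40 = 100% on the second.

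**5. How likely is a discrepancy?** The documents give no migration rate. If p is the chance that a tube is correctly placed at first and incorrectly placed later, the chance of at least one such patient is 1 − (1 − p)^N. With p assumed to be 5%, that is 1 − 0.95^40 = 0.871. But p is not the migration rate. The synopsis allows placement in the stomach or the small intestine, so a tube can move and still be correctly placed. If 5% of tubes migrate and one in five of those leaves a permitted site (both assumed), p = 0.05 × 0.2 = 0.01 and the chance is 1 − 0.99^40 = 0.331. The result is driven by assumptions that the documents cannot settle.

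**The case for a change.** The best case for a change is that the wording is cheap, the rate is the whole primary result, and a definition is better fixed before data are seen. The rule about 35 follow-up completers also suggests that the later location matters, yet no named output uses it.

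Part of this stands. Neither definition states its image or window, and a sentence saying so would do no harm. But the sentence one would write is the reading in steps 1 and 2, so it would not alter how those patients are classified. Follow-up location, migration and repositioning are collected, and the descriptive summaries in 2.4 have room for them.

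Two details remain unstated. The first is a patient who misses follow-up. If 35 of 40 return and all 35 are successes, the rate is 35/35 = 100% among those assessed, and 35/40 = 87.5% only if each missing patient counts as a failure. That would fail patients with a correct first X-ray and no recorded event. The opposite choice, counting them as event-free, is also an assumption. Giving the number assessed for adverse events beside the rate is normal practice and shows the reader what is known.

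The second is which image decides if more than one X-ray is taken within five hours. The reading above does not settle this. The reported placement attempts and tube replacement events help the reader see such cases, and each moves the rate by one patient.

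**Conclusion.** No change to the plan is needed. The endpoint leaves out a detail that its own wording and the visit schedule supply: correct position on the X-ray within five hours of placement, and no guidance-related adverse event through the 20-48 hour visit. The passages on location describe different tasks at different visits and do not contradict each other.

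A patient classified differently would move the rate by 2.5 points at N = 40 or 2.0 points at N = 50. With no hypothesis, threshold or comparator arm, that affects a descriptive percentage and no error rate or decision rule. The conclusion assumes that analysts take the endpoint's name and unrestricted adverse-event clause at face value, and that the report shows how many patients had the follow-up assessment. It would need another look if the success rate were later to be tested against a fixed criterion.

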### 2.2 SAMPLE SIZE DETERMINATION

This feasibility trial will include forty (40) to fifty (50) patients completing the Procedure Visit (NasoEnteral Tube placement) and at least five operators. ENvizion nasoenteral feeding tubes will be placed in 5 run-in subjects prior to enrollment of the remaining subjects. All enrolled subjects (run-in subjects and trial subjects) will be included in the final analysis. Patients or patients' LAR who chose not to participate after informed consent but prior to procedure, and patients who because of system malfunction or because of undiscovered or unreported physical reasons (e.g. deteriorating health, anatomical anomalies, mechanical obstruction, etc.) cannot complete the Procedure Visit (NasoEnteral Tube placement) will be considered Screen Failures, not be considered in the total patient count, but will be reported in the ITT dataset as defined below. If less than 35 patients will complete the Follow-up Visit (confirmation of tube tip anatomical location), an enrollment of another 5 patients will be considered.

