# 2.3 POPULATIONS FOR ANALYSES

Populations that will be analyzed include the following:

- Intention-to-Treat (ITT) Analysis Dataset (i.e., all enrolled participants)
- Per-Protocol Analysis Dataset: defines enrolled patients for whom no protocol deviations were noted
- Full Cohort Dataset: includes the ITT population plus the Run-in patients

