### 2.4 STATISTICAL ANALYSES

The procedure success will be calculated for all populations. Additional descriptive statistics will be presented as appropriate using means, standard deviations, medians and ranges for the continuous variables and as counts and percentages for categorical variables.

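### Placements that fail through system malfunction or anatomy are classed as Screen Failures, with no rule scoring them as procedure failures and no analysis set made up of attempted placements

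*Combined protocol and SAP*

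**What the plan says.** Section 2.1 defines procedure success, the only primary endpoint, as "NET tube can be placed in the correct anatomical position without occurrence of guidance-related adverse events". The Synopsis gives the same definition.

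Section 2.2 then names two groups. The first is patients, or their representatives, who decline after consent but before the procedure. The second is "patients who because of system malfunction or because of undiscovered or unreported physical reasons" cannot complete the Procedure Visit; the examples given include deteriorating health, anatomical anomalies and mechanical obstruction. Both groups "will be considered Screen Failures, not be considered in the total patient count, but will be reported in the ITT dataset as defined below". The Synopsis agrees that screen failures fall outside the 40-50 subjects.

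Section 2.3 defines three sets: ITT (everyone enrolled), Per-Protocol (enrolled, no deviations noted) and a third, "Full Cohort Dataset: includes the ITT population plus the Run-in patients". Section 2.4 adds: "The procedure success will be calculated for all populations".

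On when a patient becomes enrolled, the Synopsis says of the Procedure Visit: "Informed consent will be affirmed and the patient will be considered enrolled". A footnote to Table 1 qualifies this: "Affirmation of informed consent is only required if procedure visit is independent of screening visit".

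**The concern.** The endpoint asks whether the tube can be placed with the system. If insertion is attempted and cannot be completed because the system malfunctions or the anatomy prevents it, the answer for that patient is no. Section 2.2 instead labels that patient a Screen Failure, the status it also gives to someone who never reached the procedure. The second group is itself mixed: a patient who deteriorates may have been stopped before any attempt, and the text does not separate such cases from failed attempts.

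Three things are then left open:

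- whether being reported in ITT means being counted in the denominator or only listed;
- whether a non-completed placement is scored as a failure;
- which of the three sets carries the primary result.

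Reporting is purely descriptive, so the choice of denominator largely determines the result. As written, that choice can be made after the outcomes are known.

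**Working it through.** **Inputs from the documents.** 40 to 50 patients completing the Procedure Visit, including 5 run-ins (Synopsis; section 2.2). The Synopsis states that the sample size has no statistical basis, so there is no planned figure to reproduce.

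**Inputs assumed.** The documents give no rate of non-completion or withdrawal. Let *n* be the number of completers, *s* the successes among them, *k* the non-completed attempts and *w* the withdrawals before the procedure.

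**Step 1: does any defined set equal attempted placements?**

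- *ITT.* Section 2.2 puts pre-procedure withdrawals into it, so it contains people never attempted. This is in tension with its definition as everyone enrolled: when the Procedure Visit is separate, enrolment follows affirmation of consent at that visit, and earlier withdrawals would not have reached it. When the two visits coincide no affirmation is required, and the status of a withdrawal is unclear. ITT also appears to omit run-ins, since Full Cohort is formed by adding them to ITT, although section 2.2 counts run-ins among all enrolled subjects.
- *Full Cohort.* This restores the run-ins but keeps the withdrawals. It equals attempted placements only if nobody withdraws or is stopped before an attempt.
- *Per-Protocol.* This is defined by absence of deviations, which is a different criterion.

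None of the three is defined as attempted placements.

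**Step 2: how far does the scoring of non-completions move the rate?** Leaving them out gives *s*/*n*; scoring them as failures gives *s*/(*n* + *k*). The drop is *s*/*n* − *s*/(*n* + *k*). Intervals are exact (Clopper-Pearson) 95%.

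| *k* | 40 of 40 completers succeed | 38 of 40 completers succeed |
|---|---|---|
| 0 (or left out) | 40/40 = 100% (91.2-100) | 38/40 = 95.0% (83.1-99.4) |
| 1 | 40/41 = 97.6% (87.1-99.9) | 38/41 = 92.7% (80.1-98.5) |
| 4 | 40/44 = 90.9% (78.3-97.5) | 38/44 = 86.4% (72.6-94.8) |
| 7 | 40/47 = 85.1% (71.7-93.8) | 38/47 = 80.9% (66.7-90.9) |

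The drops are 2.4, 9.1 and 14.9 points in the first column and 2.3, 8.6 and 14.1 points in the second. With 50 completers, all successful, and *k* = 4, the rate is 50/54 = 92.6% (82.1-97.9), a drop of 7.4 points.

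**Step 3: what do withdrawals add?** Take *n* = *s* = 40 (run-ins included), *k* = 5, *w* = 5:

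- unscored outcomes dropped: 40/40 = 100%
- attempted placements, non-completions failed: 40/(40 + 5) = 40/45 = 88.9%
- Full Cohort, every Screen Failure a non-success: 40/(40 + 5 + 5) = 40/50 = 80.0%

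One dataset gives three rates spanning 20 points, and the text rules out neither the highest nor the lowest.

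**The case against.** The best defence is that these patients do not vanish. Section 2.2 reports them in ITT, section 2.4 calculates success in every population, and a patient whose tube was not placed does not meet the endpoint, so the natural reading makes them non-successes. On this view, removal from the patient count is only a recruitment rule (recruit until 40-50 complete), and only a clarifying sentence is missing.

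Part of this stands. The patients are not excluded from every set, and the count rule can be read as a recruitment rule. But scoring them as failures is an inference, and the Screen Failure label points the other way. Nor does that reading rescue the rate: if everyone in ITT without a placed tube is a non-success, people who declined before the procedure count as failures of the system. If ITT patients without a placement are only listed, true failures drop out.

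Three further points are fair. The non-completion counts are assumed; only the shift of roughly 2 points per case follows from the numbers of patients. There is no hypothesis or threshold, so no pass/fail decision changes. And reporting all sets side by side might expose differing rates, though with no primary set named the reader would not know which to take as the result.

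**Conclusion.** The concern holds. Section 2.2 gives failed placements a status that conflicts with the endpoint, no scoring rule is written, and no defined set matches attempted placements. Confidence in this reading of the text is high. The size is conditional: with 40 completers it is about 2 points for one non-completed placement, about 9 for four and 14 to 15 for seven, all on assumed counts. If every attempted placement is completed and nobody exits before an attempt, the scoring gap has no effect. The point should be fixed because procedure success is the only primary result of a study that the Synopsis describes as providing confirmatory evidence, although no decision rule depends on it.

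**What to change.** - **Section 2.2:** limit Screen Failure to patients who withdraw, deteriorate or are found ineligible before any insertion attempt. List them separately and keep them out of the procedure-success denominator.
- **Section 2.3:** name as the primary set all patients, run-ins included, in whom placement with the ENVUE System was attempted or was prevented by system malfunction at the Procedure Visit. The malfunction cases belong there even without an insertion, because it was the system under test that failed.
- **Scoring:** count every non-completed placement in that set as a procedure failure and tabulate the reasons, so that a reader can separate malfunction from anatomy or obstruction.
- **Synopsis:** align the text on screen failures. The target of 40-50 completers can stay as a recruitment rule.

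The cost is a wording change in these three places, with no extra patients or data. The one drawback is that the reported success rate may be slightly lower.
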